## 6.4 Dose intensity (DI) and Relative Dose Intensity (RDI)

An observed dose intensity (ODI) will be derived for each subject who receives the study drug based on how it was actually administered. A planned dose intensity (PDI) will also be derived based on the protocol-specified schedule of the study drug.

For ODI it is calculated as:

[figure not shown]
ODI = 
$$\frac{\text{Actual total dose}}{\text{Actual total duration of treatment exposure (days)}}$$

For PDI it is calculated as:

PDI 
$$=$$
  $\frac{\text{Planned total dose over protocol specified}}{\text{Actual total duration of treatment exposure (days)}}$ 

RDI is defined as: RDI =  $(ODI/PDI) \times 100\%$ .

The RDI will be summarized based on the study drug administration form in EDC. Ruxolitinib administered before the first dose of navitoclax is considered as prior study treatment therapy collected in the Study Cancer Prior Systemic Therapies (Myelofibrosis)

form in EDC for Cohort 1 (Cohorts 1a and 1b). Ruxolitinib administered after the last dose of navitoclax for Cohort 1 (Cohorts 1a and 1b) is considered as post-study treatment collected in Post Study Drug Systemic Therapies form in EDC.

The actual total duration of treatment exposure in the above equations is defined as the last dose date minus first dose date + 1 for navitoclax or ruxolitinib, respectively. Descriptive statistics will be presented for navitoclax (for all Cohorts) and ruxolitinib (for Cohort 3, Cohort 1a and Cohort 1b) respectively.

Number and percentage of subjects who have dose reductions or interruptions, will be summarized.

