#### Definition of First Date of and Last Date of Study Treatment

First date of study treatment is the date of the first dose of navitoclax. Last date of study treatment is the date of the last dose of navitoclax.

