#### 8.5.1.6 Post Baseline Red Blood Cell Transfusion

Post Baseline Red Blood Cell transfusion (for any reason) evaluation period is from after the first dose of study drug to earliest day of on or before the last dose of study drug + 30 days, or the start of post-study treatment.

Post baseline transfusion independent rate will be calculated as the proportion of subjects who achieved PRBC transfusion independent during the treatment period. PRBC Transfusion independent is defined as a period of at least 12 weeks (≥ 84 days) with no PRBC transfusions during the evaluation period. In addition, the rate of conversion will be calculated as proportion of subjects being post-baseline PRBC transfusion independent from baseline PRBC transfusion dependent.

The duration of PRBC transfusion independent will also be summarized for overall and by transfusion status at baseline (transfusion dependent and transfusion independent). The duration of transfusion independence is defined as the first time period that a subject received no PRBC transfusions for at least 12 weeks ( $\geq$  84 days). The descriptive

statistics (median and range) will be provided for the duration of transfusion independence.

Incidence rate of PRBC transfusion/subject/month, defined as total number of PRBC transfusion from all subjects divided by total duration of treatment from all subjects (months).

Time from first date of study treatment to the first time receiving 2 or more units of PRBC transfusion will be summarized.

Above endpoints will be analyzed in the Full Analysis Set.

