## 9.2.5.3 Transfusion Requirements During Study Treatment

Number of subjects who received at least a total of two units (total number of transfusion units) of PRBC transfusion or any Platelet transfusions after first dose of Navitoclax to 30 days after last dose of Navitoclax will be summarized by Transfusion type (platelet, PRBC). The Total number of transfusions (Sum of number of transfusion) among all subjects will be summarized.

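### The PRBC transfusion rate in SAP 8.5.1.6 counts events over a window that can run 30 days past last dose but divides by treatment duration, so as written it is biased upward by a modest amount that varies by cohort

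*SAP*

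**What the plan says.** SAP 8.5.1.6 opens with a single evaluation period for post-baseline PRBC transfusion. It starts after the first dose of study drug and runs "to earliest day of on or before the last dose of study drug + 30 days, or the start of post-study treatment".

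Later in the same section the incidence rate per subject per month is defined as "total number of PRBC transfusion from all subjects divided by total duration of treatment from all subjects (months"). That sentence does not restate a window for the transfusions, and the section does not define duration of treatment.

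Elsewhere the SAP ends treatment at last dose:

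- SAP 6.2 computes duration of study drug, for each drug, from first to last dose date plus one day.
- SAP 6.4 says: "The actual total duration of treatment exposure in the above equations is defined as the last dose date minus first dose date + 1".
- SAP 7.1 says: "Last date of study treatment is the date of the last dose of navitoclax".

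Two other provisions bear on the size of the gap. SAP 6.4 says: "Ruxolitinib administered after the last dose of navitoclax for Cohort 1 (Cohorts 1a and 1b) is considered as post-study treatment". It gives no matching rule for Cohort 3. SAP 9.2.5.3 summarises transfusion counts, without a rate, over the period "after first dose of Navitoclax to 30 days after last dose of Navitoclax".

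**The concern.** A rate per unit of person-time needs events and time at risk from the same period. Here a transfusion 20 days after the last dose can enter the numerator, while those 20 days do not enter the denominator. Such transfusions will be in the data, because Protocol Appendix C (Table 6) records transfusion status at the 30-day safety visit.

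The error runs in one direction. It also depends on how long subjects were treated and how long their post-dose tails were, and both can differ by cohort. SAP 8.1 presents efficacy results by cohort, so two cohorts with the same underlying transfusion rate could report different figures. PRBC and platelet transfusion requirement is also a listed safety evaluation (SAP 3.4), so readers will look at this number.

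**Working it through.** The documents state no transfusion rate, event count or person-time, so there is no planned figure to reproduce. The check is algebra on the definitions, followed by assumed ranges.

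**Inputs from the SAP**

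- Numerator window: after first dose to the earlier of last dose + 30 days or start of post-study treatment (8.5.1.6).
- Denominator: total duration of treatment (8.5.1.6), ending at last dose (6.2, 6.4, 7.1).

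**Inputs assumed**

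- Mean treatment of 84 to 504 days.
- 25% to 100% of subjects with a full 30-day tail, the rest with none.
- The same drug's last dose closes both windows, so no tail exceeds 30 days.

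**Formulas.** Let T be a subject's treatment time, *tail* the evaluation time after last dose, and N the transfusions in the evaluation period, split into N_on (up to last dose) and N_tail.

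- Rate as written: N / sum(T).
- Rate matched to the evaluation period: N / sum(T + tail).
- Ratio of the two: sum(T + tail) / sum(T) = 1 + sum(tail)/sum(T).
- Ratio to the on-treatment rate N_on / sum(T): 1 + N_tail/N_on.

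Neither ratio can be below 1. The first does not depend on the transfusion rate in the tail. The two coincide when the transfusion rate is constant across both periods.

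**Every subject with a full tail (upper bounds)**

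- Mean 84 days (12 weeks): 30/84 = 35.7%.
- Mean 168 days (24 weeks): 30/168 = 17.9%.
- Mean 336 days (48 weeks): 30/336 = 8.9%.

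**Only a share f of subjects with a full tail.** The excess is 30f / mean T.

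| Mean treatment (days) | f = 25% | f = 50% | f = 100% |
|---|---|---|---|
| 168 | 4.5% | 8.9% | 17.9% |
| 336 | 2.2% | 4.5% | 8.9% |
| 504 | 1.5% | 3.0% | 6.0% |

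**Mixed cohort (illustrative).** Take 10 subjects treated for 28 days and 10 for 168 days, all with a 30-day tail, plus 10 ongoing at 504 days with no tail.

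- sum(T) = 280 + 1,680 + 5,040 = 7,000 days.
- sum(tail) = 20 × 30 = 600 days.
- Ratio = 7,600/7,000 = 1.086. A true rate of 1.00 per month is reported as 1.086.

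**If the rate changes after last dose.** Suppose transfusions in the tail occur at k times the on-treatment rate. With a full tail and 168 days of treatment, the ratio to the on-treatment rate is 1 + 30k/168. This gives 1.000 at k = 0, 1.089 at k = 0.5, 1.179 at k = 1 and 1.357 at k = 2. The ratio to the matched evaluation-period rate stays at 1.179 throughout.

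**The case against.** The strongest reply is that this is loose wording and no stated figure is wrong. The SAP 6.4 definition is given for the dose-intensity equations, and SAP 6.2 defines duration of study drug, a slightly different term. SAP 8.5.1.6 itself refers to subjects who "achieved PRBC transfusion independent during the treatment period" and then defines that endpoint over the evaluation period. SAP 9.2.5.3 is headed as covering study treatment yet runs 30 days past it. The authors may have meant matching windows, and the SAP leaves programming detail to a separate programming plan. This shows that the text is ambiguous. It does not remove the mismatch, because no provision limits this numerator to last dose or extends this denominator to the evaluation period.

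The objection on size stands in full. A reader might infer that the reported rate will be a third too high, or doubled by early discontinuations: a subject treated for 28 days with a full tail has a factor of 58/28 = 2.07. The SAP does not average subject-level rates, though. It pools events and time, and short-treated subjects add little time to the pool. Tails also end at post-study treatment. In Cohort 1 continued ruxolitinib counts as such, so a tail there may be close to zero. Death shortens a tail, and subjects still on treatment at data cutoff have none.

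A reader might also infer that the cohorts cannot be compared on transfusion burden. That goes too far. The study is non-randomized and plans no formal testing, the cohorts differ in prior therapy and regimen, and the rate is one descriptive figure in an exploratory section. SAP 3.3 lists transfusion independence as an endpoint and does not list this rate.

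**Conclusion.** The point holds in limited form. As written, the pooled PRBC rate mixes an evaluation-period numerator with a last-dose denominator, and the resulting bias can only be upward. The excess is about 1% to 18% if mean treatment lies between 168 and 504 days, 25% to 100% of subjects have a full 30-day tail and the transfusion rate is constant. The figures of 36%, 18% and 9% at 12, 24 and 48 weeks are upper bounds on the same constant-rate basis, with a full tail in every subject.

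The size varies by cohort with treatment duration and tail length, so descriptive rates set side by side are distorted to that extent.

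One further uncertainty affects the 30-day limit. SAP 4.0 lets study drug mean both drugs in the combination cohorts, while SAP 7.1 dates study treatment by navitoclax alone. If a Cohort 3 subject stayed on ruxolitinib after navitoclax, one literal reading would make the gap longer than 30 days.

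Transfusion independence, conversion, time to first receipt of two or more units, the SAP 9.2.5.3 counts, and all primary and secondary endpoints are unaffected.

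**What to change.** Amend SAP 8.5.1.6 so that both parts of the rate use one window. Either option is valid:

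1. Keep the evaluation period for the numerator and divide by its summed length: first dose to the earliest of last dose + 30 days, start of post-study treatment, death or data cutoff, in months. Death and data cutoff are not among the end points now listed and should be added, since no transfusion can be counted after them.
2. Count only transfusions up to last dose and keep treatment duration as the denominator. This is closer to the protocol's exploratory endpoint, which concerns transfusion during study treatment (Protocol 5.3.3).

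In either case, state which drug's last dose defines the window in the combination cohorts, and use the same choice in numerator and denominator.

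The cost is one or two sentences and a small programming change, with no new data. There is a trade-off: the first option brings off-drug time into the rate, and the second drops transfusions given soon after stopping. The SAP 9.2.5.3 counts would still cover those.

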#### 8.5.1.7 Duration of Anemia Response

Duration of anemia response will be summarized by baseline transfusion status.

For subjects who were transfusion independent at baseline and achieved anemia response, the evaluation period for duration of anemia response is from achieving anemia response to 30 days after last dose of study treatment. Duration of anemia response is defined as number of days from the first date of achieving anemia response described in Table 6 to the date of loss anemia response as described in Table 7.

Table 6. Date of First Anemia Response for Duration of Anemia Response

Transfusion Status at baseline	Date of First Response
TI	On the first date observing hemoglobin level increase by $\geq 2$ g/dL from baseline without receiving PRBC transfusion within the last 2 weeks or any erythropoietin, erythropoietin mimetics within 4 weeks prior to the increased hemoglobin level
TD	On the first date observing no PRBC transfusion for at least 12 weeks

Table 7. Event and Censoring Condition for Duration of Anemia Response

[figure not shown]
Transfusion Status at baseline	Event/Censor	Date of Event/Censor
TI	Event: 1) decrease in hemoglobin level by 2 g/dL or more from the hemoglobin level at the first occurrence of achieving anemia response, or 2) need for PRBC transfusion before disease progression for the bleeding event* which was unrelated to navitoclax/ruxolitinib or 3) use of any erythropoietin, erythropoietin mimetics within 30 days of last dose of study drug	Earliest date of events
	Censor: if no above-mentioned events observed within 30 days of last dose of study drug	The last date of hemoglobin assessment after achieving anemia response, 30 days post last dose of study treatment, start of post-study treatment, disease progression, or death, whichever is earlier.  Date of achieving anemia response will be the censor date if no hemoglobin assessment is obtained after achieving anemia response.

\* Bleeding event is defined as a treatment emergent hemorrhage event from narrow search of Standardized MedDRA Queries (SMQ). PRBC occurring between the start of bleeding event and end/ongoing will be considered as need for PRBC transfusion for bleeding.

For subjects who were transfusion dependent at baseline, the duration of anemia response is defined as the 1st time period that a subject received no PRBC transfusions for at least 12 weeks ( $\geq$  84 days). The descriptive statistics (median and range) will be provided for the duration of anemia response.

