# 8.0 Efficacy Analyses

#### 8.1 General Considerations

The primary analysis population for primary endpoint is the Full Analysis Set. Unless otherwise specified, the secondary efficacy endpoints and exploratory efficacy endpoints will be analyzed in Full Analysis Set.

All efficacy results will be presented by cohort unless stated otherwise. For all analyses, unless otherwise specified, data collected after the cutoff date will be excluded from statistical analysis. All spleen volume related endpoints described in Section 3.0 will be based on the assessments from the central review of the radiographic images by an Independent Review Committee (IRC) as described in the protocol.

abbyie Navitoclax/ABT-263

Navitoclax/ABT-263 M16-109 – Statistical Analysis Plan Version 4.0 – 31 January 2023

All response rates and the corresponding 95% confidence interval (Cl) using the Clopper-Pearson method will be provided.

For the analyses of all time-to-event endpoints, survivorship functions will be estimated using Kaplan-Meier product-limit methodology. If reached, median time-to-event and its 95% CI will be presented.

For the analyses of all continuous endpoints, such as change from baseline in score, the scores will be summarized with baseline mean, visit mean, mean change from baseline, mean percentage change from baseline, standard deviation, and the corresponding 95% CIs.

Baseline measurement related to each efficacy endpoint for analysis has been described in Section 7.0.

[figure not shown]
The post-study treatment refers to Post Study Drug Systemic Therapies for Myelofibrosis, Post Study Drug Radiation Therapy and Post Study Drug Transplant. The disease progression (DP) refers to relapse or progressive disease in the Disease Response Assessment Form.

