#### 8.4.1.2 Anemia Response

Anemia response rate is defined as the proportion of subjects who achieved anemia response.

Baseline hemoglobin mentioned below is defined in Section 7.2.2. The transfusion dependency status (transfusion independent and transfusion dependent) mentioned below

are based on investigators reporting in the Study Cancer History Form according PRBC transfusion events ( $\geq 6$  units within 12 weeks and  $\geq 1$  unit within 28 days) prior to the start of study treatment.

For a subject who is transfusion independent (TI) at baseline with hemoglobin value < 10 g/dL, the subject will be considered as achieving anemia response if the post baseline hemoglobin level increases by  $\ge 2 \text{ g/dL}$  from baseline without receiving PRBC transfusion (for any reason) within 2 weeks and without any erythropoietin, erythropoietin mimetics within the last 4 weeks prior to the increase in hemoglobin level by  $\ge 2 \text{g/dL}$  was observed. Hemoglobin values after 30 days post last date of study treatment, the start of post-study treatment or disease progression whichever is earlier will not be considered in the analysis of anemia response.

For a subject who is transfusion dependent (TD) at baseline, anemia response is defined as a period of at least 12 consecutive weeks without PRBC transfusion after the first dose of study drug and on or prior to 30 days post last dose of study drug, the start of post-study treatment, disease progression or death, whichever occurs earlier.

[figure not shown]
Subjects who are baseline transfusion independent with baseline hemoglobin of  $\geq 10$  g/dL will not be included in the analysis since these subjects are not evaluable for anemia response.

Anemia response rate will also be summarized for all subjects who are evaluable for anemia response in the Full Analysis Set and by transfusion dependency status at baseline.

Missing post-baseline anemia response in Full Analysis Set applicable to evaluation of anemia response are considered as non-responders of anemia response.

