## Table B-3. Summary of Molecular Remission

	Molecular Remission Requirements			
Molecular Remission Category	Must be analyzed in peripheral blood granulocytes Requires confirmation by repeat testing within 6 months			
Complete Molecular Remission	Eradication of a pre-existing abnormality			
Partial Molecular Remission	$\geq$ 50% decrease in allele burden (to qualify for PR: must have $\geq$ 20% mutant allele burden at baseline)			

[figure not shown]
[figure not shown]

Table B-4. Summary of Progression/Relapse Criteria

Progression/Relapse Category	Progression/Relapse Criteria				
Progressive Disease	At least 1 of the following:				
	• Appearance of a new splenomegaly that is palpable at least 5 cm below the left costal margin (LCM)*				
	• A $\geq$ 100% increase in palpable distance below LCM, for baseline splenomegaly of 5 – 10 cm*				
	
 
A 50% increase in palpable distance below LCM, for baseline splenomegaly of > 10 cm*
 
				
	• MRI showing a ≥ 25% increase in spleen volume from baseline				
	
 
Leukemic transformation confirmed by a bone marrow blast count of ≥ 20%
 
				
	• A peripheral blood blast content of $\geq 20\%$ associated with an absolute blast count of $\geq 1 \times 10^9/L$ that lasts for at least 2 weeks				
Relapse	At least 1 of the following:				
	No longer meeting criteria for at least Clinical Improvement after achieving Complete Response, Partial Response or Clinical Improvement				
	• Loss of anemia response persisting for ≥ 1 month				
	• Loss of spleen response persisting for ≥ 1 month				
Cytogenetic/Molecular Relapse	Re-emergence of a pre-existing cytogenetic or molecular abnormality that is confirmed by repeat testing				

LCM = left costal margin

\* Requires confirmation by MRI with a  $\geq$  25% increase in spleen volume from baseline.

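### The hemoglobin rule that ends an anemia response (SAP Table 7, event 1) is measured from the first-response value, while response is measured from baseline, so the duration does not track time in response

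*SAP*

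**What the plan says.** **Response.** SAP 8.4.1.2 covers subjects who are transfusion independent at baseline with hemoglobin below 10 g/dL: "the subject will be considered as achieving anemia response if the post baseline hemoglobin level increases by" at least 2 g/dL from baseline, without recent PRBC transfusion or erythropoietin. Table 6 in SAP 8.5.1.7 dates the response the same way: "On the first date observing hemoglobin level increase by" at least 2 g/dL over baseline.

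**Loss.** Table 7 lists three events, and the earliest counts:

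1. a "decrease in hemoglobin level by 2 g/dL or more from the hemoglobin level at the first occurrence of achieving anemia response";
2. "need for PRBC transfusion before disease progression for the bleeding event", where the bleed is unrelated to either study drug;
3. "use of any erythropoietin, erythropoietin mimetics within 30 days of last dose of study drug".

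**Censoring.** With no such event, the subject is censored at the earliest of several dates: the last hemoglobin assessment, 30 days after the last dose, or "start of post-study treatment, disease progression, or death, whichever is earlier".

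**Progression.** SAP 8.1 widens that term: "The disease progression (DP) refers to relapse or progressive disease in the Disease Response Assessment Form". Under Table B-4 in SAP Appendix B, one of the relapse criteria is "Loss of anemia response persisting for" at least 1 month. That table attaches no hemoglobin value to loss.

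**The concern.** Response and loss have different reference points. A subject enters response by crossing baseline + 2 g/dL, but no event is tied to dropping back below that line. Event 1 looks instead at the distance fallen from whatever value happened to be seen at the first qualifying visit. Two subjects with the same baseline and the same later hemoglobin can then have different durations because of a single earlier reading.

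Events 2 and 3 do not fill the gap. One needs a bleeding event and the other needs erythropoietin use, so neither picks up hemoglobin drifting back toward baseline.

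The study has an exploratory objective on the onset, magnitude and duration of response, with anemia named. A reported median duration would naturally be read as time spent in response by the SAP's own criterion, and Table 7 does not measure that.

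**Working it through.** The documents state no duration, event count or target for this endpoint, so there is no figure to reproduce. The check is threshold arithmetic, followed by illustrative paths.

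**Step 1: where event 1 fires.** Let r be the rise over baseline at first response, with r ≥ 2. Event 1 needs a fall of at least 2 from that value, so it fires when the current rise is ≤ r − 2. The response criterion itself fails when the current rise is < 2. The gap between the two levels is 2 − (r − 2) = 4 − r.

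| r (g/dL) | Event 1 level over baseline | Gap below the +2 criterion, 4 − r |
|---|---|---|
| 2.0 | 0.0 | 2.0 |
| 2.2 | 0.2 | 1.8 |
| 2.5 | 0.5 | 1.5 |
| 3.0 | 1.0 | 1.0 |
| 3.5 | 1.5 | 0.5 |
| 4.0 | 2.0 | 0.0 |
| 4.5 | 2.5 | −0.5 |
| 5.0 | 3.0 | −1.0 |

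Event 1 is laxer than the response criterion for r < 4, about equal to it at r = 4, and stricter for r > 4.

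**Step 2: one case each way.**
- Baseline 8.0, first response 10.1, later 8.2. The fall is 10.1 − 8.2 = 1.9, so there is no event 1, yet the subject is only 8.2 − 8.0 = 0.2 above baseline.
- First response at +4.2, later +2.1. The fall is 4.2 − 2.1 = 2.1, so event 1 fires, yet +2.1 still meets the response criterion.

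**Step 3: size on assumed paths.** Visits follow the protocol hematology schedule: Weeks 1, 2, 3, 4, 6, 8, 12, 16, 20, 24, then every 12 weeks. Assume hemoglobin climbs linearly to its peak rise at Week 12, holds to Week 24, then falls linearly.

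For a peak of +2.5, the Week 8 value is 2.5 × 8/12 = 1.67, so first response is at Week 12 with r = 2.5. Event 1 needs a rise ≤ 0.5, and the response criterion fails at a rise < 2. At 0.05 g/dL per week:
- Week 36 is 2.5 − 0.05 × 12 = 1.9, which is below +2, so the criterion-based duration is 36 − 12 = 24 weeks.
- Week 60 is 2.5 − 0.05 × 36 = 0.7, which is not yet event 1.
- Week 72 is 2.5 − 0.05 × 48 = 0.1, which is event 1, so the Table 7 duration is 72 − 12 = 60 weeks.

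| Assumed peak | Decline (g/dL/week) | r at first response | Table 7, event 1 (weeks) | Below +2 (weeks) | Excess (weeks) |
|---|---|---|---|---|---|
| +2.5 | 0.05 | 2.5 | 60 | 24 | 36 |
| +2.5 | 0.1 | 2.5 | 36 | 24 | 12 |
| +2.5 | 0.2 | 2.5 | 24 | 24 | 0 |
| +4.5 | 0.05 | 2.25 | 114 | 78 | 36 |
| +4.5 | 0.1 | 2.25 | 66 | 54 | 12 |
| +4.5 | 0.2 | 2.25 | 42 | 42 | 0 |

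A high peak does not by itself make r large. With a peak of +4.5, the first value over +2 is at Week 6 (4.5 × 6/12 = 2.25), so the laxer side of the rule applies. These paths have no measurement noise, no persistence condition and no relapse censoring.

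**Step 4: relapse.** An investigator-recorded relapse for loss of anemia response counts as disease progression under SAP 8.1. In Table 7 disease progression is a censoring date. The subject therefore leaves the risk set at the moment the outcome of interest is recorded, without contributing an event. That censoring is informative, and SAP 8.1 prescribes Kaplan-Meier for time-to-event endpoints. Read literally, Table 7 also censors only subjects with no event within 30 days of the last dose, so a subject who relapses, stays on treatment and later meets event 1 is dated at that later event.

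**The case against.** The best defence has four parts.

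**Other routes out of response.** A reader might infer that a response ends only when hemoglobin falls. That is not what Table 7 says: events 2 and 3 also end it, and a subject recorded as relapsed is censored and, absent an event, accrues no more time. This stands as a limit on the point. It does not repair event 1, because neither other event detects hemoglobin drift and censoring a recorded loss is not the same as counting it.

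**Direction.** A reader might infer that every duration is overstated. The documents do not support that, since for r > 4 the rule shortens duration. Because r is the first value at or above +2 and early visits are frequent, values below 4 seem likelier, but that is an expectation and not a documented fact.

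**Appendix B.** A reader might infer that Table 7 contradicts Table B-4. It cannot be shown to. Table B-4 gives no hemoglobin value for loss and serves as a relapse criterion, not as a definition of duration.

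**A deliberate buffer.** The SAP version history lists changes to the duration of anemia response in versions 1.1, 2.0 and the 3.0 draft. A 2 g/dL fall is also the documents' size for worsening anemia, although measured from baseline. Duration of SVR35 (SAP 8.5.1.2) has a buffer too, requiring a 25% rise from nadir. A guard against single noisy values is reasonable. But the SVR35 rule also requires that the reduction is below 35%, so the response criterion must be lost, and it counts relapse as an event. Table 7 does neither, and the SAP gives no reason for the difference.

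**Conclusion.** The point holds as an asymmetry in the only hemoglobin-based loss event. The loss level is baseline + (r − 2) where the response level is baseline + 2. The effect is longer durations for 2 ≤ r < 4 and shorter ones for r > 4. Separately, censoring relapse for loss of anemia response can push a Kaplan-Meier estimate upward.

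The threshold arithmetic follows from the SAP alone. The size does not. The 0 to 36 weeks comes from assumed linear paths, and a different decline rate or within-subject variability would change it. Under continuous observation, a first response at +2.2 with a fall of 0.1 g/dL per week would give (2.2 − 2)/0.1 = 2 weeks against 2/0.1 = 20 weeks. A reader might infer a tenfold inflation from that, but the documents give neither the path nor the rate, and the visit schedule narrows the ratio. Any overstatement is relative to the SAP's own response criterion, since no other numeric definition of loss is given.

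The scope is limited to transfusion-independent responders, an exploratory endpoint, and an estimation-only study. SVR35 at Week 24 and the anemia response rate do not change. The point is worth correcting because the reported duration would otherwise not mean what its name says.

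**What to change.** - **Event 1.** Redefine it as hemoglobin less than 2 g/dL above the SAP 7.2.2 baseline, persisting for a stated period and dated at the first such value. At least 1 month is a natural choice. It borrows the period in Table B-4 as a convention, because that table sets no hemoglobin level. Since visits are 12 weeks apart after Week 24, also say how a last low value with no later measurement is treated.
- **Relapse.** Count relapse recorded for loss of anemia response as an event, and state which date applies when both it and event 1 occur. The documents do not show whether the response form records the criterion behind a relapse; if it does not, say how this relapse will be identified.
- **Sensitivity analysis.** Keep the current Table 7 rule as a sensitivity analysis, with its rationale.

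The cost is a wording change and the reprogramming of one exploratory derivation from hemoglobin and disease-assessment data already collected. Most reported durations would be expected to become shorter.
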